23.3.1 Primary outcome

The primary outcome (KOOS-4 at 24 months) will be compared using a mixed-effects linear model to calculate the mean difference between treatment groups. Treatment, baseline KOOS-4 and planned lateral extra-articular procedure will be incorporated as fixed effects and recruiting site as a random effect. Results will be presented as estimates and 95% CIs whenever possible. A sensitivity analysis will be conducted that removes participants aged 20 years or younger at the time of completing baseline KOOS-4. Sensitivity to missing data will also be explored using informative missing to confirm tolerance to differential mechanisms (using a pattern-mixture model approach).

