15.3 Randomisation methodology

Participants will be randomly allocated to one of two treatment options (1:1) via automated, secure (encrypted), web-based randomisation provided by the Oxford Clinical Trials Research Unit (OCTRU) using a REDCap platform.

Random allocation will be implemented using a minimisation algorithm with stratification factors: preinjury Tegner score (2 groups (0-6, 7-10)), planned lateral extra-articular procedure (yes, no) and site. The minimisation algorithm will be seeded with several allocations and a non-deterministic probabilistic element will be introduced to prevent predictability of the treatment allocation.

Patients not randomised in theatre will be managed along the normal standard of care pathway.

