23.2 Sample Size/Power Calculations

The sample size calculation was premised upon a 1:1 randomised parallel group trial design with an analysis of the primary outcome (KOOS-4) using mixed-effects linear model adjusted for randomisation variables and baseline KOOS-4. Standard nominal 2-sided 5% significance level was adopted, and the power for detecting a between group difference of 8 and 9 points in the KOOS-4, was assessed for a missing data allowance of 15%.

We considered a variety of scenarios varying the adjustment for baseline correlation and desired statistical power. (See Table 4 below for a selection)

Table 4 – Sample size scenarios; all based upon 2-sided 5% significance level, 1:1 allocation continuous outcome, pooled SD of 20, and non-central-t distribution calculation [Stata power two means command]

No.	Target difference	Statistical Power	Missing data allowance	Adjusted for baseline	Sample size required (overall)
1	8	80	15%	No	236
2	8	90	15%	No	314
3	9	80	15%	No	186
4	9	90	15%	No	248
5	8	80	15%	Yes	204
6	8	90	15%	Yes	272
7	9	80	15%	Yes	162
8	9	90	15%	Yes	214

An overall sample size of 236 and 186 is required for 80% power for a difference of 8 points and 9 points respectively given a pooled standard deviation (SD) of 20 points. Equivalent 90% power, required number of observations are 314 and 248 respectively.

However, the expected sample size required is lower given the planned adjustment for baseline KOOS-

4 score as the effective variability is reduced. Implementing this using the formula provided by Borm⁽³⁹⁾ using a correlation between baseline and follow-up score of 0.37 leads to requiring only 204 and 272 for 80% and 90% power for a target difference of 8 points or equivalently 162 and 214 (all other assumptions and inputs as before) for 9 points difference. Therefore, we have opted for a sample size of 214 (no. 8, table 2) randomised participants which allows for 15% missing data for a target difference of 9 points (at 90% power). This sample size also ensures more than 80% power for a target difference of 8 points (no. 5, Table 2).

We anticipate that 25% of those who consent to be assessed as unsuitable for repair intra-operatively, we expect approximately 286 will need to be consented. The intraoperative assessment at arthroscopy has been shown to be crucial to determine the repairability of the ligament and reduce failure rate $^{(40)}$.

Justification of sample size inputs

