Target difference: The selected target difference was informed by a review of the relevant literature conducted for the ACL SNNAP study which was updated for this submission. The Minimal Important Change (MIC) for the KOOS score is 8-10 points. Estimates of the Minimal Detectable Changes (MDC) for the two KOOS subscales most relevant for ACL deficiency (ACLD) vary between 5 and 12 points (Symptoms= 5-8.5 and Sport/Rec=6-12)⁽⁴¹⁾. A more recent review of the literature specifically for studies assessing meaningful values in the KOOS and other candidate patient reported outcome score for ACL tears or traumatic meniscus injuries) did not indicate a different value for KOOS or that another outcome had better research on meaningful differences⁽⁴²⁾. Study findings agree with a search in PubMed review conducted for the study funding proposal (13 June 2023) of studies assessing clinical important differences in the KOOS score. The recently published ACL-SNNAP demonstrated that a mean difference of 8 points is possible between interventions and that this magnitude of difference related to tangible differences in other knee specific patient reported outcome, generic measure of patient satisfaction (would you have the treatment again if you could go back, and assessment of knee after versus before). We note that while figures such as 0.2 or 0.3 SD are regularly quoted patientreported quality of life measures do differ in their underlying properties, and estimates for important differences in the literature have varied⁽⁴³⁾. It has been suggested that 0.5 SD is a more appropriate standard deviation (SD) for the minimally important difference for quality of life⁽⁴⁴⁾, which would equate to a target difference of around 10 points here if implemented (i.e. "Cohen's effect size" distribution approach). We have used target difference values of 8 and 9 points when considering various sample size scenarios which the current evidence on important differences and responsiveness suggest are reasonable estimates of a minimal clinically important difference (MCID) for the KOOS-4 outcome.

Standard deviation: The (pooled) SD value of 20 was based upon the observed value in the ACL SNNAP study at 18 months (19.9 pooled SD). Given the target population in ACL STARR is more homogenous the SD may well be slightly lower.

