23.3.2 Secondary outcome(s)

Secondary outcomes will be analysed in a similar manner to the primary outcome. KOOS over 24 months, EQ-5D-5L and EQ-VAS, emotional functioning questions taken from KQoL-26, and postoperative pain will use mixed-effects linear regression, like that of the primary outcome, that also incorporates a time-by-treatment effect as a fixed effect and patient as a random effect. All five KOOS domains will be quantified at each time point. Pain-NRS at 3 and 6 weeks will be analysed using a simpler multiple linear regression model adjusted for site using robust variance. Modified Tegner will be compared at each time point in a similar manner. Graft failure and re-operation will be analysed using survival analysis methods: Kaplan-Meier curves, and Cox proportional hazards models (or logrank test if insufficient events). The Cox model will be adjusted with mixed-effects, in line with the analysis approach for other outcomes, if there are enough events. If not, the model will be unadjusted⁽⁴⁵⁾. Patient satisfaction questions will be analysed using logistic regression and adjusted for minimisation factors in line with other outcomes. Intervention-related complication (up to 24 months) will be presented using descriptive statistics, by type, frequency and treatment arm.

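### The primary model in section 23.3.1 leaves out pre-injury Tegner group, one of the three minimisation factors, and so disagrees with section 23.2; the cost is at most a slightly conservative test

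*Protocol*

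**What the plan says.** Four places in the protocol bear on the covariates of the primary model.

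- Section 15.3 (Randomisation methodology) names the minimisation factors: "preinjury Tegner score (2 groups (0-6, 7-10)), planned lateral extra-articular procedure (yes, no) and site".
- Section 23.2 (Sample Size/Power Calculations) describes the primary analysis as "using mixed-effects linear model adjusted for randomisation variables and baseline KOOS-4".
- Section 23.3.1 (Primary outcome) gives the operative list: "Treatment, baseline KOOS-4 and planned lateral extra-articular procedure will be incorporated as fixed effects and recruiting site as a random effect".
- Section 23.3.2 (Secondary outcomes) says the satisfaction questions are "adjusted for minimisation factors in line with other outcomes".

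Section 15.3.1 gives the reason for each factor. Tegner is there to balance high and low pre-injury activity. Of LEP it says only that its status as a confounder is unknown. No section explains why Tegner is dropped from the primary model while LEP is kept.

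**The concern.** Section 23.3.1 fixes a covariate list that sections 23.2 and 23.3.2 contradict. This is more than a detail left for the statistical analysis plan, because no such plan can agree with both descriptions. Section 23.1 has the study statistician write that plan and finalise it before the final data lock, and Table 2 in section 18.1 shows that the statisticians have access to allocations. It is better not to leave two candidate covariate sets open for the primary test.

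The statistical reason for analysing by the factors used to allocate is well known. Minimisation makes the arms alike in Tegner group, so differences between Tegner groups contribute little to the real sampling variation of the treatment difference. A model without Tegner still counts that variation as residual noise. Its standard error can then exceed the true one, which gives a confidence interval that is too wide and a test that rejects less often than its nominal 5%.

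**Working it through.** **Step 1. Set the lists side by side.**

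| Section | Tegner group | Planned LEP | Site | Baseline KOOS-4 |
|---|---|---|---|---|
| 15.3, minimisation | yes | yes | yes | n/a |
| 23.2, model assumed | yes (as a randomisation variable) | yes | yes | yes |
| 23.3.1, primary model | **no** | yes | yes (random) | yes |
| 23.3.2, satisfaction | yes (as a minimisation factor) | yes | yes | not stated |

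**Step 2. Reproduce the planned sample size.** The inputs are all in section 23.2: "Standard nominal 2-sided 5% significance level was adopted"; 90% power for 9 points; an SD of 20 ("The (pooled) SD value of 20 was based upon the observed value in the ACL SNNAP study at 18 months"); "using a correlation between baseline and follow-up score of 0.37"; and 15% missing data.

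- Non-central t for two means gives 105 per arm, 210 in total.
- Baseline adjustment factor: 1 − 0.37² = 0.8631, and 210 × 0.8631 = 181.3, so 182 analysed.
- Missing data: 181.3 / 0.85 = 213.2, which rounds up to 214.

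The figure of 214 is reproduced. The only covariate gain it counts is the baseline correlation. Nothing was credited for Tegner, so including or omitting Tegner leaves the planned number unchanged.

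**Step 3. Effect of omission on the standard error.** The residual SD after baseline is 20 × √0.8631 = 18.58 (variance 345.24). With 182 analysed 1:1, the model standard error without Tegner is 18.58 × √(4/182) = 2.755.

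Let p be the share of residual variance explained by Tegner group. The protocol does not give p; I assume 0.01 to 0.10. With Tegner perfectly balanced:

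- true SE = 2.755 × √(1 − p)
- ratio of model SE to true SE = 1/√(1 − p)
- type I error = 2 × [1 − Φ(1.96/√(1 − p))]
- power without Tegner = Φ[(9 − 1.96 × 2.755) / true SE]
- power with Tegner = Φ[9 / true SE − 1.96]
- implied gap between Tegner groups, with a 50:50 split = 2 × 18.58 × √p

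| p | Gap (points) | SE ratio | Type I error | Power without | Power with |
|---|---|---|---|---|---|
| 0 | 0 | 1.000 | 5.0% | 90.4% | 90.4% |
| 0.01 | 3.7 | 1.005 | 4.9% | 90.6% | 90.7% |
| 0.05 | 8.3 | 1.026 | 4.4% | 91.0% | 91.8% |
| 0.10 | 11.8 | 1.054 | 3.9% | 91.6% | 93.1% |

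For p = 0.10, the true SE is 2.755 × 0.9487 = 2.613. Power without Tegner is Φ(3.60/2.613) = Φ(1.378) = 91.6%. Power with Tegner is Φ(3.444 − 1.96) = Φ(1.484) = 93.1%. The difference is about 1.5 points. These are normal approximations.

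**Step 4. Check by simulation.** Minimisation was simulated with an assumed assignment probability of 0.8, 20 sites, 214 randomised, 15% missing at random and 4,000 runs per setting. The data had no site effect and the fitted models no site term.

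- Tegner gap of 10 points: type I error 4.3% without Tegner and 5.1% with it; power at 9 points 91.8% and 92.8%.
- Tegner gap of 15 points, beyond the range in the table: model SE about 7% to 9% too large without Tegner, type I error 3.7%, power 91.7% without and 94.9% with.
- Mean error of the treatment estimate: no more than 0.1 point in any setting, with or without Tegner.

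At a gap of 5 points or less, any difference in type I error is within simulation noise.

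**The case against.** The strongest reply is that the effect may be nil and is harmless in direction. The documents give no association between Tegner group and 24-month KOOS-4 once baseline KOOS-4 and LEP are in the model. With no association there is no error at all. The upper end of the assumed range needs a gap of about 11.8 points between activity groups, more than the 9-point target and the 8 to 10 point important change cited in section 23.2. All of this stands, and it limits the point to a minor one.

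A reader might infer more than the protocol supports:

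- **That the primary standard error and p-value will certainly be wrong.** They may be overstated, and only if Tegner is prognostic given the other covariates.
- **That the false-positive risk rises or the estimate is biased.** The type I error falls below 5%, and the simulation shows negligible bias.
- **That the trial is underpowered or 214 is wrong.** The 214 never relied on Tegner, and power without it stays above 90% throughout the table. What is forgone is a possible bonus.
- **That every secondary model inherits the omission.** Section 23.3.2 adjusts satisfaction for the minimisation factors, gives the 3- and 6-week pain score a model adjusted for site only, and allows an unadjusted Cox model when events are few.
- **That the complete-case analysis is left exposed.** Nothing in the protocol links activity level to loss to follow-up, and section 23.3.1 already plans a pattern-mixture sensitivity analysis.

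It can also be said that section 23.1 presents the protocol as a summary, with full detail in the statistical analysis plan. That does not remove the conflict, because the plan would inherit two incompatible statements.

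**Conclusion.** The inconsistency is real and nothing in the protocol resolves it: section 23.3.1 omits one of three minimisation factors that section 23.2 says are adjusted for, and the satisfaction wording in section 23.3.2 does not fit it either. If Tegner group explains 1% to 10% of residual KOOS-4 variance, the primary standard error would be about 0.5% to 5% too large, the type I error about 4.9% to 3.9%, and at most about 1.5 points of available power would be forgone. These figures assume near-perfect balance on Tegner and, where stated as gaps in points, an even split between the two groups; looser balance makes the effect smaller. The sample size, the planned power and the unbiasedness of the estimate are unaffected. This is a minor correction worth making because it is free.

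**What to change.** In section 23.3.1, insert pre-injury Tegner group (0-6, 7-10) among the fixed effects, next to baseline KOOS-4 and planned LEP, and keep site as the random effect. Sections 15.3, 23.2 and 23.3.1 then agree.

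In section 23.3.2, include Tegner group only in the models described as like the primary model or as adjusted for the minimisation factors. Leave the site-only pain model and the unadjusted Cox fallback as written.

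If the omission is intended, the alternative is to say why in section 23.3.1 and correct the wording in sections 23.2 and 23.3.2.

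The cost is one phrase, carried into the statistical analysis plan before it is finalised. No new data are needed, because the Tegner group must be known before a participant can be randomised, and the sample size does not change.

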23.3.2 Secondary outcome(s)

Secondary outcomes will be analysed in a similar manner to the primary outcome. KOOS over 24 months, EQ-5D-5L and EQ-VAS, emotional functioning questions taken from KQoL-26, and postoperative pain will use mixed-effects linear regression, like that of the primary outcome, that also incorporates a time-by-treatment effect as a fixed effect and patient as a random effect. All five KOOS domains will be quantified at each time point. Pain-NRS at 3 and 6 weeks will be analysed using a simpler multiple linear regression model adjusted for site using robust variance. Modified Tegner will be compared at each time point in a similar manner. Graft failure and re-operation will be analysed using survival analysis methods: Kaplan-Meier curves, and Cox proportional hazards models (or logrank test if insufficient events). The Cox model will be adjusted with mixed-effects, in line with the analysis approach for other outcomes, if there are enough events. If not, the model will be unadjusted⁽⁴⁵⁾. Patient satisfaction questions will be analysed using logistic regression and adjusted for minimisation factors in line with other outcomes. Intervention-related complication (up to 24 months) will be presented using descriptive statistics, by type, frequency and treatment arm.

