9 OBJECTIVES AND OUTCOME MEASURES

9.1 Aim

The primary aim of the study is to establish whether ACL repair provides more benefit than ACL reconstruction in patients with recent proximal ACL ruptures of the knee.

Research Question

Does acute ACL repair provide superior clinical outcomes (as measured by the Knee injury and Osteoarthritis Outcome Score (KOOS-4)) at 24 months, and is it cost effective compared to ACL reconstruction in patients with recent proximal ACL ruptures?

Primary and Secondary objectives/outcomes measures

The primary and secondary objectives are outlined below in Section 9.2. The primary outcome measure is the aggregated and averaged score of four of the five sub-scales of KOOS (KOOS-4): pain, symptoms, activities of daily living, and sport and recreation function, at 24 months post randomisation. The secondary outcomes are the five individual KOOS sub-scale scores (KOOS-5), repair/ graft re-rupture rate, re operation, health-related quality of life, time to return to work, time to return to sport, emotional functioning and cost effectiveness (including time away from paid employment and education). Measures include KOOS at 6 and 12 months post-randomisation and over the 24 months period, complications, graft failure, re-operation, EQ-5D-5L, emotional functioning questions taken from KQoL-26, post operative pain, and resource usage. A subjective measure will also be collected on the Surgery CRF to understand 'surgeon confidence' in the ACL surgery performed (recorded on a scale of 1-10).

Activity level will be assessed using the Tegner Scale, graded from 1 (low activity levels) to 10 (professional level). In addition, the Tegner has been modified as follows: three columns with the headings of (1) activity level before your injury, (2) current level of activity (today) and (3) level you expect to return to, were added to the baseline form. At 6, 12 and 24 months, the Tegner contains one answer column as follows: current level of activity (today).

_

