17.2.2 Follow-up assessments/subsequent visits

Follow up for study purposes will be by patient self-reported questionnaire completed using a web-based data collection system (REDCap). The option of being able to fill out the follow-up questionnaires in a hard copy and returning via post will also be available. The questionnaires will contain the following outcome measures: KOOS, EQ-5D-5L/VAS, emotional functioning questions taken from KQoL-26, Tegner, and will be sent out at 6-, 12- and 24-months post randomisation to all participants. Patient satisfaction and return to sport outcome measures will be added to the 12- and 24-month questionnaires. The questionnaires will also ask participants if they have returned to see a health care professional or been admitted to hospital in relation to complications with their study knee, and time away from paid employment and education. The central CTU study team will follow up any complications reported by participants with the research team at the participant's local hospital. Further details about the event will be collected and recorded on a complications form.

A final readmission checklist will be undertaken by the Research staff on hospital records at 24 months post randomisation to ensure that all complications data is collected from all participants (i.e. those who had not returned a questionnaire). Data from any readmission events identified will be recorded in a "Complications" CRF. The physiotherapy case report form (PCRF) will be used to record the number of post-operative rehabilitation physiotherapy sessions attended, and the date of discharge from physiotherapy. If a participant attends community-based physiotherapy, the number of sessions attended will be reported via the patient questionnaires.

Patients will also be asked to complete a pain numerical rating scale to report their post operative pain at 3- and 6-weeks post randomisation. A link to complete the score online will be sent by either SMS, email or post. Contact preferences will be recorded in REDCap after consent.

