23.3 Description of Statistical Methods

The statistical analyses will be performed once the 24 months follow up has been reached by the last patient and sufficient time has been allowed for data collection and cleaning.

Results will be reported in line with the Consolidated Standards of Reporting Trials (CONSORT) statement and any appropriate extensions and will be described fully in a separate Statistical Analysis Plan. The SAP will be finalised prior to un-blinding of the data to clinical investigators and after consultation with investigators and other relevant stakeholders.

Nominal 2-sided 5% significance level will be used throughout. Subgroup analyses will be indicated as exploratory and non-planned analyses as "post-hoc".

Intention-to-treat (ITT) will be the main analysis strategy and will be adopted for the primary and all secondary outcomes. In other words, the analysis will principally be focussed on a treatment policy estimand. As patients are randomised in theatre, following surgeon confirmation of suitability, non-compliance is expected to be minimised and intercurrent events more limited than in a typical NHS based surgical study (e.g. no post-randomisation timing of surgery mediation). However, some repairs may still be abandoned, perioperatively and post randomisation. Rates of compliance will be monitored throughout the study, including the pilot phase. Two secondary analysis populations will therefore be conducted on the primary outcome: a per-protocol analysis, that mirrors ITT but excludes patients with major protocol deviations, and an as-treated analysis, where patients are classified according to the treatment received. These secondary analyses will assess robustness of ITT analysis and any deviation from routine clinical practice. The handling of such events will be agreed in advance of conducting the analysis and detailed in the SAP.

The main analysis will be conducted using a complete case approach with no planned imputation for missing data. An independent Data and Safety Monitoring Committee (DSMC) will meet early in the study to agree its terms of references. They will review confidential interim analyses of the stop-go criteria and monitor within patient correlation of KOOS-4 scores between baseline and 24 months and compliance to randomised treatment.

It is anticipated that all statistical analysis will be undertaken using Stata (StataCorp LP, www.stata.com) or other validated statistical software.

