23.4 Inclusion in analysis

The principal analysis will be performed on the as-randomised ("intention to treat") population, analysing participants with available outcome data in their randomised groups, regardless of adherence. Secondary populations will also be analysed as defined in Section 23.3.

The study will be reported in line with CONSORT guidelines.

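### Time to return to sport and to work fall under a complete-case linear-model default that does not accommodate participants not yet returned, and time to return to work has no measure of its own

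*Protocol*

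**What the plan says.** **Outcomes.** The list of secondary outcomes in protocol section 9.1 includes "time to return to work, time to return to sport, emotional functioning and cost effectiveness".

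**Analysis.** Section 23.3.2 opens with a general rule: "Secondary outcomes will be analysed in a similar manner to the primary outcome". The primary outcome, in section 23.3.1, "will be compared using a mixed-effects linear model to calculate the mean difference between treatment groups". Section 23.3.2 then goes through the outcomes: linear models for KOOS, EQ-5D-5L and EQ-VAS, emotional functioning and pain, a similar comparison for Tegner, logistic regression for satisfaction, and description for complications. For events it says "Graft failure and re-operation will be analysed using survival analysis methods". Neither return outcome appears in that list.

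**Missing data and analysis set.** Section 23.3: "The main analysis will be conducted using a complete case approach with no planned imputation for missing data". Section 23.4 describes the principal analysis as "analysing participants with available outcome data in their randomised groups, regardless of adherence".

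**Collection.** Time to return to sport has an entry in section 9.3 and a row in Table 1, by patient questionnaire at 12 and 24 months. Time to return to work has neither. The nearest item, in section 17.2.2, is "time away from paid employment and education". Section 9.1 places that item within cost effectiveness and lists time to return to work separately.

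**The concern.** A return time is a time-to-event outcome. Someone who has not returned by the last questionnaire has a time known only to exceed the follow-up, and a linear model for a mean difference needs a number for each person. If the default and the complete-case rule are applied to such an outcome as they stand, the natural result is a mean among those with an observed time. Membership of that group is decided after randomisation and may be affected by the operation, so the groups compared are no longer the randomised ones. This would sit badly with section 23.3, which adopts intention to treat for all secondary outcomes.

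These outcomes matter to the trial's case. The lay summary (section 5) reports that the patient focus groups stressed getting back quickly to sport and work, and section 8 gives faster return to activity as a potential advantage of repair.

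For work there is a further difficulty: if no date or status of return is asked for, no analysis method can recover it later.

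**Working it through.** **Step 1. Which rule applies.** Setting section 9.1 against section 23.3.2, the two return outcomes are on the list of outcomes and absent from the list of methods. Survival methods are assigned to two other outcomes only. What remains is the default sentence, which leads to the mean-difference model of 23.3.1, with 23.3 and 23.4 governing who is included.

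**Step 2. What the rule does with a non-returner.** The protocol does not say how such a participant is coded. There are two ways to fit a linear model:
- Treat the time as missing. The complete-case rule then removes the person.
- Set the time to 24 months. This estimates a restricted mean, which is a sensible quantity, but the protocol does not state it. It also gives no value for someone who had not returned at 12 months and sent no later form.

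**Step 3. Number of participants.** The plan's own sample size gives the evaluable number. A difference of 9, SD 20, two-sided 5% and 90% power need 105 per arm (noncentral t). Multiplying by 1 − 0.37² = 0.8631 gives 90.6, so 91 per arm, and 182 / 0.85 = 214.1, which agrees with the stated 214. The illustration uses 91 evaluable per arm.

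**Step 4. Illustration.** The protocol gives no return rates or times, so all of these are assumed: the proportion returning by 24 months, the mean time among returners, and SD 3 months with times held between 6 and 24 months. There were 4,000 simulated trials per scenario. A t-test among returners is compared with a log-rank test on all participants, non-returners being censored at 24 months.

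| Returned, A v B | Mean months among returners, A v B | Returners-only difference (A − B) | Returners-only test rejects | Log-rank rejects |
|---|---|---|---|---|
| 60% v 60% | 12 v 12 | 0.0 | 5% | 5% |
| 50% v 70% | 12 v 12 | 0.0 | 5% | 77% |
| 40% v 70% | 12 v 12 | 0.0 | 5% | 98% |
| 50% v 70% | 11 v 12 | −1.0 | 39% | 61% |

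In the second row the returners-only test uses about 91 × 0.5 + 91 × 0.7 = 109 of 182 participants.

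**Step 5. The same scenarios counting everyone up to 24 months.** The restricted mean is (proportion returned × mean time) + (proportion not returned × 24).
- Second row: A = 0.5 × 12 + 0.5 × 24 = 18.0 and B = 0.7 × 12 + 0.3 × 24 = 15.6. A is 2.4 months worse, while the returners-only difference is zero.
- Fourth row: A = 0.5 × 11 + 0.5 × 24 = 17.5 and B = 15.6. A is 1.9 months worse, while the returners-only comparison makes A look about 1 month better.

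**Step 6. Return to work.** No simulation is offered. Appendix 2 lists return to work among the early-stage aims of rehabilitation, so the proportion still off work at 24 months may be small. The point for work rests on the text: the outcome is named in 9.1, has no measure or time point in 9.3 or Table 1, and differs from the time-away item that 9.1 lists elsewhere.

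**The case against.** A reader might infer that the protocol excludes non-returners and compares only those who returned. It does not say that. The default wording is loose, and the same paragraph departs from it to suit the type of data, with Cox models for events and logistic regression for satisfaction. An unlisted time-to-event outcome could as naturally join the Cox group. A participant who reports not having returned has answered the question, so the complete-case sentence need not remove them. Sections 23.1, 23.3 and 23.8 leave details to an analysis plan that is not shown, and that plan could assign a censored analysis. All of this stands, and it is why the point concerns what the stated rule fails to accommodate and not an exclusion that the protocol announces.

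Tegner level is also collected at 6, 12 and 24 months and compared at each time point, so people who never go back to sport still contribute to a measure of activity. That softens the consequence for sport, but it does not measure time to return.

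The illustration rests wholly on assumed rates, uses gaps of 20 to 30 percentage points, and fits sport only. It shows the direction of the risk and not its likely size. The questionnaire itself is not shown either, so its time-away item might allow a return date to be derived. The protocol does not say that it does.

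What the deferral to an analysis plan cannot answer is the return-to-work gap. Naming an outcome without a measure is an inconsistency within the protocol, and an analysis plan written after the forms are in use cannot supply an answer that was never collected.

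**Conclusion.** The point holds in this form: the only analysis rule reaching two named time-to-event outcomes is a linear mean-difference model on complete cases, which, as written, does not accommodate participants who have not returned by 24 months. If the comparison were limited to observed return times, it could miss a difference in the proportion returning or point the wrong way. How far is unknown, because the documents give no return rates; the figures of about 5% against 77% to 98% depend on the assumed gaps and on non-returners being treated as missing. Separately, and without any assumption about rates, time to return to work is listed as an outcome but has no measure or time point. No figure in the protocol changes, and the primary outcome is unaffected. This should be put right, the collection item first, because it cannot be mended after follow-up.

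**What to change.** 1. In section 23.3.2, add both return outcomes to the Kaplan-Meier and Cox sentence. Measure time from randomisation, which takes place in theatre. Censor participants not yet returned at their last completed questionnaire, at most 24 months.
2. Report the proportion returned at 12 and 24 months by arm, beside the time-to-event result.
3. For work, define who is at risk: participants in paid work before injury, with those in education treated separately. Recruitment starts at age 14, and without this definition people with no job would be counted as not having returned.
4. Add return-to-work status and date to the existing questionnaires, with matching rows in section 9.3 and Table 1. Otherwise remove time to return to work from the secondary outcomes in section 9.1 and keep time away from work as the economic measure.

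The cost is a wording amendment, with whatever approval the changed questionnaire needs, and one added questionnaire item. It needs no extra participants or visits.
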